4.1 Description of study design

Patients treated with curative intent either in the post-operative or definitive setting with high dose radiotherapy (≥ 50 Gy) with or without chemotherapy will be eligible. There will be one treatment group with each patient serving as their own control. Patients would have their salivary output measured before radiotherapy, 3 weeks after the start of radiotherapy, and at the end of radiotherapy (6 weeks). Patients who demonstrate more than a 50% decrease in

saliva flow rates will enter the treatment phase of the trial. Based on expert experience, we estimate that half the treated patients will exhibit a decrease of 50% or more in flow rate. These affected patients will then receive the planned dose of everolimus **once a day for 5 days, starting two weeks after the completion of radiotherapy**. Salivary output measurements will be obtained prior to everolimus administration and at completion of the 5 day everolimus course and at 1 month, 3 months and 6 months after the completion of radiation or chemoradiation therapy.

It is our expectation that because of the short exposure to everolimus (a total of 5 days only), the well described everolimus related toxicities will not develop.

However, following discussions with the company (Novartis), two dose levels will be evaluated: a starting dose of 5 mg po daily, will initially be evaluated in a cohort of 3 patients.

For the purpose of this trial, dose-limiting toxicity (DLT) is defined as an everolimus-related grade 3 or higher AE.

Toxicity will be graded based on the Common Terminology Criteria for Adverse Events (CTCAE) Version4.03.

(<http://www.hrc.govt.nz/sites/default/files/CTCAE%20manual%20-%20DMCC.pdf>)

As mentioned, we will start treating enrolled patients on the lower dose level.

-If no DLT occurs, will proceed with dose escalation to the full FDA-approved dose (10 mg po daily) [in this case, total number of patients in the trial: 13; 3 in the 5 mg cohort, 10 in the 10 mg cohort].

-If 1 DLT occurs, cohort will be expanded to additional 3 patients; and if another DLT occurs in this expanded cohort, no escalation to full dose (10 mg po daily) will be attempted, and cohort will be expanded to 10 patients [in this case, total number of patients in the trial: 10; all in the 5 mg cohort];

and if no additional DLT occurs in the expanded cohort, dose escalation to full dose (10 mg po daily) will follow [in this case, total number of patients in the trial: 16; 6 in the 5 mg cohort, 10 in the 10 mg cohort].

-If 2 DLT occur, no escalation to full dose (10 mg po daily) will be attempted, and cohort will

be expanded to 10 patients.) [in this case, total number of patients in the trial: 10; all in the 5 mg cohort].

As a result of these possibilities, total number of patients included in this phase 0, proof of principle trial can range from a minimum of 10 to a maximum of 16 total patients.

Maximum number of 16 patients will occur if a DLT occurs in one of the first 3 patients in the 5 mg cohort, and no DLT occurs in the additional 3 expanded cohort patients (for a total of 6 patients in the 5 mg cohort). Subsequently, 10 additional patients will be enrolled in the 10 mg cohort, for a maximum total of 16 patients.

Procedures:

Stimulated Salivary flow measurements:

Patients will undergo both unstimulated whole saliva collection and stimulated whole saliva collection at each visit. Stimulated whole saliva collection measures the ability of the gland to respond to an external stimulus, which is necessary when eating. It is also likely that this measurement will correlate with swallowing difficulties. The average stimulated saliva output for a normal person is 1.5–2.0 mL/min and some studies have used a \leq 0.5–0.7 mL/min cutoff for hyposalivation determination.

- Patients must fast overnight, however, they may eat 2 hours prior to their scheduled appointment. They are encouraged to perform oral hygiene immediately after eating their meal to remove any remaining food particles, but no later than the two hour time period before their scheduled appointment. They also need to refrain from smoking two hours prior to their scheduled appointment.
- Saliva production is stimulated by the patient chewing unflavored gum base or paraffin wax (1-2g) for 1 minute. The saliva is then collected by the patient spitting into pre-weighed specimen cups during this time frame

Unstimulated Whole Saliva Flow Rate and Collection

- 1) On the day of saliva collection, patient is to not have eaten for 2 hours prior to their scheduled collection appointment
 - a) No enteral feedings for 2 hours prior to collection appointment

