Premature patient withdrawal	Point/time when the patient exits from the study prior to the planned completion of all study treatment administration and/or assessments; at this time all study treatment administration is discontinued and no further assessments are planned, unless the patient will be followed for progression and/or survival
Stop study participation	Point/time at which the patient came in for a final evaluation visit or when study treatment was discontinued whichever is later
Study treatment	
Includes any drug or combination of drugs in any study arm administered to the patient (subject) as part of the required study procedures, including placebo and active drug run-ins.
 
In specific examples, it is important to judge investigational treatment component relationship relative to a study treatment combination; study treatment in this case refers to the investigational and non-investigational treatments in combination.

Study treatment discontinuation	Point/time when patient permanently stops taking study treatment for any reason; may or may not also be the point/time of premature patient withdrawal
Supportive treatment	Refers to any treatment required by the exposure to a study treatment, e.g. premedication of vitamin supplementation and corticosteroid for pemetrexed disodium.
Variable	Identifier used in the data analysis; derived directly or indirectly from data collected using specified assessments at specified time points

Schema

Step 1¹

R
E
G
I
S
T
E
R

RT or chemoRT
administration

Step 2²

R
E
G
I
S
T
E
R

Everolimus
Administration³

↓↓↓↓

CORRELATIVE STUDIES⁴

¹ Patients with locally advanced squamous cell carcinoma of the Head and Neck treated with curative intent either in the post-operative or definitive setting with high dose radiotherapy (RT ≥ 50 Gy) with or without chemotherapy (chemoRT) will be eligible

² Verify eligibility for everolimus treatment. Patients with clinically severe gland dysfunction (i.e., those with loss of at least 50% of the pre-radiotherapy value) will be eligible for everolimus treatment.

³ Everolimus (5 or 10 mg) po qd, x 5days only, starting 2 weeks after definitive treatment completion

⁴ Saliva flow rates and xerostomia surveys will be obtained at baseline, after 3 and 6 weeks of RT/chemoRT, prior to everolimus administration, at completion of the 5 day everolimus course and at 1,3 and 6 months after RT/chemoRT completion

1 Background

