6.3 Concomitant medications

Patients must be instructed not to take any medications (over-the-counter or other products) during the protocol treatment period without prior consultation with the investigator. The investigator should instruct the patient to notify the study site about any new medications he/she takes after the start of study drug. All medications (other than study drug) and significant non-drug therapies (including physical therapy and blood transfusions) taken within 28 days of starting study treatment through the 30-day safety follow up visit should be reported on the CRF.

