7.1 Study flow and visit schedule

Table 7-1 Visit evaluation schedule

	Screening / Baseline	RT Day 22	RT Day 43	Post RT day 15	Post RT day 22	Post RT week 6	Post RT week 14	Post RT week 26
Visit no.	1	2	3	4	5	6	7	8
Treatment days*	-21 to -1							
Demography/informed consent (D)	X							
Inclusion/exclusion criteria (D)	X							
Relevant medical history/current medical conditions (D)	X							
Diagnosis and extent of cancer (D)	X							
Prior/post antineoplastic therapy (D)	X							
HIV history (S)	X							
Vital signs (D)	X	X	X	X	X	X	X	X
Height (D)	X							
Weight (D)	X	X	X	X	X	X	X	X
Physical examination (S)	X	X	X	X	X	X	X	X
ECOG performance status (D)	X	X			X	X	X	X
EKG ¹ (D)			X					
Correlative studies	X	X	X	X	X	X	X	X
Hematology ² (D)	X		X	X	X			
Coagulation (D)	X		X	X	X			
Biochemistry ³ (D)	X		X	X	X			
Serum Lipid Profile ⁴ (D)	X		X	X	X			
Prior/concomitant medications (D)	X			X	X			

	Screening / Baseline	RT Day 22	RT Day 43	Post RT day 15	Post RT day 22	Post RT week 6	Post RT week 14	Post RT week 26
Visit no.	1	2	3	4	5	6	7	8
Treatment days*	-21 to -1							
Everolimus ⁵				X				
HBV-DNA, HBsAg, HBs Ab, HBc Ab, HCV-RNA-PCR ⁶ (D)	X							
HBV DNA, HCV RNA-PCR ⁷ (D)	X							

* (+/- 1 day for visits 2,3,4,5; +/- 1 week for visits 6,7,8)

1. Baseline ECG is a standard 12 lead and must be performed within 21 days of first dose for patients enrolled and may be repeated at the investigator's discretion if clinically indicated
2. Hematology tests include a complete blood count (CBC). A total white blood cell (WBC) with absolute differentials (including neutrophil count plus bands, lymphocyte, monocyte, eosinophil, basophil counts), red blood cells (RBC), hemoglobin (Hgb), and a platelet count.
3. Serum Chemistry must include: BUN or uric acid, creatinine, LDH, total protein, electrolytes (sodium, potassium and calcium), total bilirubin, GGT, albumin, alkaline phosphatase, AST/sGOT fasting glucose.
4. Serum fasting lipid profile must include: total cholesterol and triglycerides. Patients should be in fasting state.
5. Everolimus is taken once daily for a total of five days, with drug dispensed at Visit 4.

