8.1 Adverse events

8.1.1 Definitions and reporting

An adverse event is defined as the appearance of (or worsening of any pre-existing) undesirable sign(s), symptom(s), or medical condition(s) that occur after patient's signed informed consent has been obtained.

Abnormal laboratory values or test results occurring after informed consent constitute adverse events only if they induce clinical signs or symptoms, are considered clinically significant, require therapy

(e.g., hematologic abnormality that requires transfusion or hematological stem cell support), or require changes in study medication(s).

Adverse events that begin or worsen after informed consent should be recorded *in the Adverse Events CRF*. Conditions that were already present at the time of informed consent should be recorded *in the Medical History page of the patient's CRF*. Adverse event monitoring should be continued for at least 30 days (or 5 half-lives, whichever is longer) following the last dose of study treatment. Adverse events (including lab abnormalities that constitute AEs) should be described using a diagnosis whenever possible, rather than individual underlying signs and symptoms. When a clear diagnosis cannot be identified, each sign or symptom should be reported as a separate Adverse Event. Adverse events will be assessed according to the Common Terminology Criteria for Adverse Events (CTCAE) version 4.0.

If CTCAE grading does not exist for an adverse event, the severity of mild, moderate, severe, and life-threatening, corresponding to Grades 1 - 4, will be used.

The occurrence of adverse events should be sought by non-directive questioning of the patient (subject) during the screening process after signing informed consent and at each visit during the study. Adverse events also may be detected when they are volunteered by the patient (subject) during the screening process or between visits, or through physical examination, laboratory test, or other assessments. As far as possible, each adverse event should be evaluated to determine:

1. The severity grade (CTCAE Grade 1-4)
2. *Its duration (Start and end dates) (add or Ongoing at End of Study for)*
3. *Its relationship to the study treatment (Reasonable possibility that AE is related: No, Yes or*
Its relationship to the study treatment (Reasonable possibility that AE is related: No, Yes, investigational treatment, Yes, the study treatment (non-investigational), Yes, both and/or indistinguishable)

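### The escalation rule sets no DLT counting period and does not require the 5 mg cohort to complete one before 10 mg opens, and the 10 mg de-escalation rule that section 11.4 refers to is not in section 9.1

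*Protocol*

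**What the plan says.** The Initial Objective (section 3) is to document the safe dose, 5 mg or 10 mg, by a 3 + 3 design. Sections 4.1, 6.1 and 9.1 state the rule in nearly the same words.

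- **What counts:** "For the purpose of this trial, dose-limiting toxicity (DLT) is defined as an everolimus-related grade 3 or higher AE". No time limit is attached.
- **No DLT in the first three 5 mg patients:** "If no DLT occurs, will proceed with dose escalation to the full FDA-approved dose (10 mg po daily)".
- **One DLT in the first three:** three more patients are treated at 5 mg, "and if no additional DLT occurs in the expanded cohort, dose escalation to full dose (10 mg po daily) will follow".
- **Two DLTs:** there is no escalation, and the 5 mg cohort grows to ten.
- **After escalation from six patients:** "Subsequently, 10 additional patients will be enrolled in the 10 mg cohort, for a maximum total of 16 patients". No DLT count is attached to these ten.

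On timing, footnote 5 of Table 7-1 says: "Everolimus is taken once daily for a total of five days, with drug dispensed at Visit 4". Section 8.1.1 says: "Adverse event monitoring should be continued for at least 30 days (or 5 half-lives, whichever is longer) following the last dose of study treatment". Section 6.3 records concomitant medication "through the 30-day safety follow up visit should be reported on the CRF", but Table 7-1 has no column for that visit. The schema has two registrations. Step 2 comes after radiotherapy, with the footnote "Verify eligibility for everolimus treatment". The Glossary, by contrast, ties enrolment to informed consent, which Table 7-1 places at screening.

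Section 11.4 refers the reader to 9.1 for escalation and de-escalation, possibly including closure, according to DLTs.

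**The concern.** A 3 + 3 rule needs to say when a patient counts as DLT-free. Here the only period in which a related grade 3 event is sought is the adverse-event period of 8.1.1, and nothing links that period to the escalation decision. The text therefore allows 10 mg to open on a provisional 0 of 3. A later related grade 3 event would make it 1 of 3. The rule would then call for three more patients at 5 mg, and it says nothing about anyone already on 10 mg.

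With three patients, one event changes the branch. There is also no later correction. Once 10 mg is open, ten patients are to be treated whatever the number of DLTs, because the de-escalation procedure that 11.4 relies on is not in 9.1. The rule governs live dosing at two sites and serves the Initial Objective, so it belongs in the protocol rather than in an analysis plan.

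**Working it through.** **Plan's own totals.** 3 + 10 = 13; 6 + 10 = 16; 10 if dosing stays at 5 mg. These agree with sections 4.1 and 9.1.

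**Timeline for one 5 mg patient (Table 7-1 and 8.1.1).**
- Doses are taken on post-RT days 15 to 19. The minimum adverse-event period ends on day 19 + 30 = 49. This is 5 + 30 = 35 days from the first dose.
- Visit 5 is day 22. It serves here only as an example of an early reading. It falls 22 − 19 = 3 days after the last dose, on drug day 22 − 15 + 1 = 8, with 49 − 22 = 27 days still to run. With the ±1 day windows on Visits 4 and 5, 25 to 29 days remain.
- These are calendar days, not shares of DLT risk. All five doses have been given by then.

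**Can a 10 mg dose fall in those 27 days?** Radiotherapy start to first dose takes 42 + 14 = 56 days.
- *Enrolled* read as consent before radiotherapy (Glossary): a new patient is at least 56 days from dosing, and 56 > 27. There is no overlap with the 30-day minimum.
- *Enrolled* read as Step 2 registration after radiotherapy (Schema): any patient who began radiotherapy 56 − 27 = 29 or more days before that reading falls due inside the period. Overlap is possible.

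**Illustrative effect on escalation.** The protocol gives neither a DLT rate nor a timing, so both are assumed. With true DLT rate p and full observation,

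E(p) = (1 − p)³ + 3p(1 − p)⁵.

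If a share f of DLTs appears only after the reading, p is replaced by (1 − f)p. This assumes that both the first three and the added three patients are read early.

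| p | full observation | f = 10% | f = 25% | f = 50% |
|---|---|---|---|---|
| 5% | 0.973 | 0.978 (+0.5) | 0.985 (+1.1) | 0.993 (+1.9) |
| 10% | 0.906 | 0.922 (+1.6) | 0.944 (+3.8) | 0.973 (+6.7) |

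Figures in brackets are percentage points, taken before rounding. The share of early 0-of-3 readings later overturned is 1 − [(1 − p)/(1 − 0.75p)]³ for f = 25%, which gives 4% at p = 5% and 8% at p = 10%. At higher assumed rates the shift grows: at f = 25%, E goes from 0.709 to 0.814 at p = 20%, and from 0.494 to 0.654 at p = 30%.

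**The 10 mg cohort.** With no rule, all ten are treated, and the expected number of DLTs is 10p: 1, 2, 3 and 4 at assumed rates of 10, 20, 30 and 40%. A 3 + 3 limit at 10 mg would halt it with probability 1 − E(p) = 0.09, 0.29, 0.51 and 0.69 at those rates.

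**Patients falling due during a wait.** From the third (or sixth) patient's first dose to the end of the period is 35 days. Accrual is not given. At an assumed 0 to 3 treated patients per month, this is 0 to 3 × 35/30.4 = 3.5, so about 0 to 4 patients.

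**The case against.** Four points have force.

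1. The Glossary ties enrolment to consent, and sections 4.1 and 9.1 say the ten patients are enrolled afterwards. On that reading no 10 mg patient is dosed before the 5 mg period has run out. This stands as one reading. It does not close the matter, because the schema registers patients for everolimus separately after radiotherapy, and the totals of 10, 13 and 16 appear to count treated patients.
2. The design is sequential, and a count of no DLTs is most naturally read at the end of the adverse-event period. That is a fair account of the likely intent. The link is still unwritten in all three statements of the rule.
3. There is other oversight. Tables 6-1 and 6-2 stop the drug for most individual grade 3 or 4 toxicities, weekly calls cover adverse events and cohort management, the DSMB gets monthly reports, and 10 mg is an approved dose. Worsening mucositis in two of the first six patients halves the dose (section 4.1). These limit the harm, but none is a DLT criterion for the cohort.
4. The protocol expects little toxicity from five doses, and the last scheduled blood tests are at Visit 5. If DLTs are rare and early, the effect is small.

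A reader might infer that the protocol opens 10 mg at Visit 5, or that 10 mg will overlap with 5 mg follow-up. The documents support neither: no section names a decision visit, and overlap depends on how enrolment is read.

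**Conclusion.** The point holds in a limited form. The escalation rule has no DLT counting period and does not require the 5 mg cohort to complete one. 10 mg could therefore start on a provisional result if dose is assigned at Step 2 registration. If assignment is at consent, there is little or no overlap. Independently of that, section 11.4 refers to a de-escalation procedure that 9.1 does not contain, so no number of DLTs at 10 mg stops or lowers dosing.

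The documents do not determine the size. The shift of 0.5 to 6.7 points rests on assumed DLT rates of 5–10%, 10–50% of DLTs appearing late, and an early reading. The larger shifts at 20–30% should not be taken as a forecast, since nothing in the protocol supports such rates for a five-day course. An amendment is worthwhile because the rule controls dosing and its correction is cheap.

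**What to change.** In 4.1, 6.1 and 9.1, state that:

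- DLTs are counted from the first dose through 30 days after the last dose.
- No 10 mg dose is given until the third (or sixth) 5 mg patient has completed that period.
- A patient who becomes due during the wait is treated at 5 mg, and any DLT in that patient counts in the escalation decision.

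Add the 30-day safety contact named in 6.3 to Table 7-1. Visit 6 is nominally day 6 × 7 = 42, before day 49, so it cannot reliably serve. No blood tests are scheduled after Visit 5, so unless some are added the contact will mainly capture clinical events.

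Put into 9.1 the 10 mg rule that 11.4 presumes. One option is the same 3 + 3 limit: two DLTs in the first three to six 10 mg patients returns dosing to 5 mg.

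**Cost.** Amendment wording, one added contact, and a wait of about 30 days after the last dose of the deciding 5 mg patient. At an assumed 0 to 3 treated patients per month, about 0 to 4 are treated at 5 mg during the wait. The totals would be restated from 13 to 13–17 and from 16 to 16–20. The branches that stay at 5 mg keep ten.

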- 9) If the patient is too dry, (dry mouth), it is possible to add the weight of the gum base to the pre-weight measure with the gum base in the cup of saliva.

Analysis of saliva: The collection tubes are weighed before and after saliva collection. The difference equates to the total mL collected which is divided by the number of minutes of collection. Saliva is stored at -80°C for further analysis on salivary protein composition at a later date (described in correlatives below).

The comorbidity of mucositis is an important consideration in this study due to the development of this condition following radiotherapy and as a side effect from chronic use of everolimus. Treatment with everolimus has been designed to begin two weeks after radiotherapy to allow radiation-induced mucositis to start improving. In a pre-clinical model,

concurrent rapamycin treatment with radiotherapy (6Gy/day X 5 days) prevents mucositis due in part to increased expression of mitochondrial superoxide dismutase (MnSOD) (Iglesias-Bartolome 2012). Given the short duration of treatment in this trial (5 days), a delay in the start of everolimus until two weeks after radiotherapy and evidence from this pre-clinical study, we postulate that mucositis will not be a major concern. Patients will be closely monitored for worsening mucositis response once treated with everolimus and if mucositis worsens in 2 out of the first 6 patients, then everolimus 50% dose reduction will be implemented.

5 Population

Patients with locally advanced squamous cell carcinoma of the head and neck, treated with curative intent either in the post-operative or definitive setting with high dose radiotherapy (≥ 50 Gy) with or without chemotherapy will be eligible. Patients will be stratified for exploratory analyses in the analysis phase on the basis of ipsilateral vs bilateral neck irradiation. There will be one treatment group with each patient serving as their own control.

This study will evaluate the response in 10 – 16 patients enrolled at both facilities: St. Joseph's Hospital and Medical Center in Phoenix and Banner – University Medical Center in Tucson (details and justification of sample size in statistical methods) to determine if the proposed everolimus dosing schedule of 5 days is sufficient to show recovery of salivary gland function to pre-treatment levels.

These data will also provide guidance on an option for a longer delivery of everolimus in patients with a partial improvement of salivary flow or an option for de-escalation of dose if a large number of patients demonstrate improvements in salivary flow at early time points.

5.1 Inclusion and Exclusion criteria

Patients must have baseline evaluations performed prior to the first dose of study drug and must meet all inclusion and exclusion criteria. Results of all baseline evaluations, which assure that all inclusion and exclusion criteria have been satisfied, must be reviewed by the Principal Investigator or his/her designee prior to enrollment of that patient. In addition, the patient must be thoroughly informed about all aspects of the study, including the study visit schedule and required evaluations and all regulatory requirements for informed consent. The written informed consent must be obtained from the patient prior to enrollment. The following criteria apply to all patients enrolled onto the study unless otherwise specified.

Inclusion criteria:

1. Age 18-75 years
2. Performance status ECOG ≤ 2
3. Adequate bone marrow function as shown by: ANC $\geq 1.5 \times 10^9/L$, Platelets $\geq 100 \times 10^9/L$, Hgb $> 9 \text{ g/dL}$;
4. Adequate liver function as shown by:
 - a. Total serum bilirubin $\leq 2.0 \text{ mg/dL}$,
 - b. ALT and AST $\leq 2.5 \times \text{ULN}$ ($\leq 5 \times \text{ULN}$ in patients with liver metastases),
 - c. INR ≤ 2 ;
5. Adequate renal function: serum creatinine $\leq 1.5 \times \text{ULN}$;
6. Fasting serum cholesterol $\leq 300 \text{ mg/dL}$ OR $\leq 7.75 \text{ mmol/L}$ AND fasting triglycerides $\leq 2.5 \times \text{ULN}$. NOTE: In case one or both of these thresholds are exceeded, the patient can only be included after initiation of appropriate lipid lowering medication;
7. Signed informed consent obtained prior to any screening procedures.
8. Patients with locally advanced squamous cell carcinoma of the head and neck, treated with curative intent either in the post-operative or definitive setting with high dose radiotherapy ($\geq 50 \text{ Gy}$) with or without chemotherapy.

Exclusion criteria:

1. Patients currently receiving anticancer therapies or who have received anticancer therapies within 2 weeks of the start of Everolimus (including chemotherapy, radiation therapy, antibody based therapy, etc.);
2. Known intolerance or hypersensitivity to Everolimus or other rapamycin analogs (e.g. sirolimus, temsirolimus);
3. Known impairment of gastrointestinal (GI) function or GI disease that may significantly alter the absorption of oral Everolimus;
4. Uncontrolled diabetes mellitus as defined by HbA1c $> 8\%$ despite adequate therapy. Patients with a known history of impaired fasting glucose or diabetes mellitus (DM) may be included, however blood glucose and antidiabetic treatment must be monitored closely throughout the trial and adjusted as necessary;
5. Patients who have any severe and/or uncontrolled medical conditions such as:
 - a. unstable angina pectoris, symptomatic congestive heart failure, myocardial infarction ≤ 6 months prior to start of Everolimus, serious uncontrolled cardiac arrhythmia, or any other clinically significant cardiac disease
 - b. Symptomatic congestive heart failure of New York heart Association Class III or IV
 - c. active (acute or chronic) or uncontrolled severe infection, liver disease such as cirrhosis, decompensated liver disease, and active and chronic hepatitis (i.e. quantifiable HBV-DNA and/or positive HbsAg, quantifiable HCV-RNA),
 - d. known severely impaired lung function (spirometry and DLCO 50% or less of normal and O₂ saturation 88% or less at rest on room air),
 - e. active, bleeding diathesis;

6. Chronic treatment with corticosteroids or other immunosuppressive agents. Topical or inhaled corticosteroids are allowed;
7. Known history of HIV seropositivity;
8. Patients who have received live attenuated vaccines within 1 week of start of Everolimus and during the study. Patient should also avoid close contact with others who have received live attenuated vaccines. Examples of live attenuated vaccines include intranasal influenza, measles, mumps, rubella, oral polio, BCG, yellow fever, varicella and TY21a typhoid vaccines;
9. Patients who have a history of another primary malignancy, with the exceptions of: non-melanoma skin cancer, and carcinoma in situ of the cervix, uteri, or breast from which the patient has been disease free for ≥ 3 years;
10. Patients with a history of non-compliance to medical regimens or who are considered potentially unreliable or will not be able to complete the entire study;
11. Patients who are currently part of or have participated in any clinical investigation with an investigational drug within 1 month prior to dosing;
12. Pregnant or nursing (lactating) women;
13. Women of child-bearing potential (WOCBP) (including female pediatric patients who are menarcheal or who become menarcheal during the treatment), defined as all women physiologically capable of becoming pregnant, must use highly effective methods of contraception during the study and 8 weeks after. Women are considered post-menopausal and not of child-bearing potential if they have had 12 months of natural (spontaneous) amenorrhea with an appropriate clinical profile (e.g. age appropriate, history of vasomotor symptoms). Highly effective contraception methods include combination of any two of the following:

Use of oral, injected or implanted hormonal methods of contraception or placement of an intrauterine device (IUD) or intrauterine system (IUS) or other forms of hormonal contraception that have comparable efficacy (failure rate $<1\%$), for example, hormone vaginal ring or transdermal hormone contraception. In case of use of oral contraception women should have been stable on the oral agent for a minimum of 3 months before taking everolimus

 - a. Total abstinence or;
 - b. Male partner sterilization. (The vasectomized male partner should be the sole partner for that subject)
 - c. Female sterilization have had surgical bilateral oophorectomy (with or without hysterectomy), total hysterectomy or tubal ligation at least six weeks prior to randomization. In the case of oophorectomy alone, only when the reproductive status of the woman has been confirmed by follow up hormone level assessment is she considered not of child-bearing potential.
14. Male patients whose sexual partner(s) are WOCBP who are not willing to use adequate contraception, during the study and for 8 weeks after the end of treatment

Screening for hepatitis B

Prior to randomization/start of Everolimus, the following three categories of patients should be tested for hepatitis B viral load and serologic markers, that is, HBV-DNA, HBsAg, HBs Ab, and HBc Ab:

- All patients who currently live in (or have lived in) Asia, Africa, Central and South America, Eastern Europe, Spain, Portugal and Greece.
[<http://wwwnc.cdc.gov/travel/yellowbook/2012/chapter-3-infectious-diseases-related-to-travel/hepatitis-b.htm>]
- Patients with any of the following risk factors:
 - known or suspected past hepatitis B infection,
 - blood transfusion(s) prior to 1990,
 - current or prior IV drug users,
 - current or prior dialysis,
 - household contact with hepatitis B infected patient(s),
 - current or prior high-risk sexual activity,
 - body piercing or tattoos,
 - mother known to have hepatitis B
 - history suggestive of hepatitis B infection, e.g., dark urine, jaundice, right upper quadrant pain.
- Additional patients at the discretion of the investigator

The management guidelines, in Section 6.2.3.10, are provided according to the results of the baseline assessment of viral load and serological markers for hepatitis B.

Screening for hepatitis C

Patients with any of the following risk factors for hepatitis C should be tested using quantitative RNA-PCR:

- known or suspected past hepatitis C infection (including patients with past interferon 'curative' treatment),
- blood transfusions prior to 1990,
- current or prior IV drug users,
- current or prior dialysis,
- household contact of hepatitis C infected patient(s),
- current or prior high-risk sexual activity,
- body piercing or tattoos.

At the discretion of the investigator, additional patients may also be tested for hepatitis C.

The management guidelines, in Section 6.2.3.10, are provided according to the results of the baseline assessment of hepatitis C viral load.

6 Treatment

